### 15.6 Analysis of Secondary Objectives

- For safety analysis, adverse events will be summarized by type and grade.
- Hazard rate estimates and 95% confidence intervals as well as Kaplan-Meier (KM) estimates will be used to summarize survival (OS), progression free survival (PFS), time to locoregional progression (TTLP) and time to distant progression (TTDP), duration of response functions over time. The median OS, PFS, TTLP and TTDP will be reported.
- The efficacy of SBRT combined with Nelfinavir with oligometastatic disease will also be determined by measuring local control of each lesion at 6 month. Each metastatic lesion will be considered a target lesion and independently evaluated for response using RECIST 1.1. The lesion will be coded as being locally controlled if it is considered stable radiographic disease or if there is evidence of a partial or complete response. Local control assessment will start at one month following completion of protocol treatment and continuous assessment will be pursued during the follow-up period. The proportion of the lesions that have a stable or better response will be estimated using generalized estimating equation. The above analyses will also be performed by metastases site (bone, liver and lung).
- Quality of life will be assessed using the Brief Pain Inventory form. An overall score will be calculated pre-treatment and at the time of the 2nd radiologic reassessment. The change in score will be evaluated with a paired t-test.
- The analysis for the correlative study will be done by Western blot. The change of phospho-Akt levels will be correlated to progression-free survival outcome.

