#### **3.2 Secondary Objectives**

To assess the toxicity of the radiosensitizer Nelfinavir used concurrently with 15 Gy of stereotactic body radiation therapy (SBRT) delivered in 1 fraction (per lesion) in patients with oligometastatic disease.

To determine local control at 6 months after SBRT delivered to a dose of 15 Gy in 1 fraction (per lesion) combined with Nelfinavir patients with oligometastatic disease.

To assess long-term clinical outcomes of this patient population after completion of SBRT in combination with Nelfinavir.

To assess quality of life following completion of SBRT in combination with Nelfinavir.

To determine the correlation between Phospho-Akt levels and lesion response rate.

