## 12.5 Nelfinavir

12.5.1 The safety of VIRACEPT (Nelfinavir mesylate) was studied in over 5000 patients who received drug either alone or in combination with nucleoside analogues. The majority of adverse events were of mild intensity. The most frequently reported adverse event among patients receiving VIRACEPT was diarrhea, which was generally of mild to moderate intensity. The frequency of Nelfinavir-associated diarrhea may be increased in patients receiving the 625 mg tablet because of the increased bioavailability of this formulation.

Adverse events occurring in patients receiving VIRACEPT in all phase II/III clinical trials and considered at least possibly related or of unknown relationship to treatment and of at least moderate severity are listed below:

*Body as a Whole:* abdominal pain, accidental injury, allergic reaction, asthenia, back pain, fever, headache, malaise, pain, and redistribution/accumulation of body fat.

*Digestive System:* anorexia, nausea dyspepsia, epigastric pain, gastrointestinal bleeding, hepatitis, mouth ulceration, pancreatitis and vomiting.

*Hemic/Lymphatic System:* anemia, neutropenia, leukopenia and thrombocytopenia.

*Metabolic/Nutritional System:* increases in alkaline phosphatase, amylase, creatinine, phosphokinase, lactic dehydrogenase, SGOT, SGPT and gamma glutamyl transpeptidase; hyperlipemia, hyperuricemia, hyperglycemia, hypoglycemia, new onset or exacerbation of diabetes mellitus, dehydration, hepatitis, jaundice, and liver function tests abnormal.

*Musculoskeletal System:* arthralgia, arthritis, cramps, myalgia, myasthenia and myopathy.

*Nervous System:* anxiety, depression, dizziness, emotional lability, hyperkinesia, insomnia, migraine, paresthesia, seizures, sleep disorder, somnolence and suicide ideation.

*Respiratory System:* dyspnea, pharyngitis, rhinitis, and sinusitis.

*Skin/Appendages:* dermatitis, folliculitis, fungal dermatitis, maculopapular rash, pruritus, sweating, and urticaria.

*Special Senses:* acute iritis and eye disorder.

*Urogenital System:* kidney calculus, sexual dysfunction and urine abnormality.

12.5.2 The following additional adverse experiences have been reported from post marketing surveillance as at least possibly related or of unknown relationship to VIRACEPT:

*Body as a Whole:* hypersensitivity reactions (including bronchospasm, moderate to severe rash, fever and edema).

*Cardiovascular System:* QTc prolongation, torsades de pointes.

*Digestive System:* jaundice.

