**6. Please rate your pain by circling the one number that tells how much pain you have right now.**

0 1 2 3 4 5 6 7 8 9 10  
No Pain Pain as bad as you can imagine

7. What treatments or medications are you receiving for your pain?

8. In the last 24 hours, how much relief have pain treatments or medications provided? Please circle the one percentage that most shows how much relief you have received.

0% 10% 20% 30% 40% 50% 60% 70% 80% 90% 100%  
No Complete  
Relief Relief

9. Circle the one number that describes how, during the past 24 hours, pain has interfered with your:

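### The quality-of-life objective rests on one uncontrolled change in a pain score, with no account of pain treatment and no rated item that reaches beyond pain

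*Combined protocol and SAP*

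**What the plan says.** Section 3.2 sets the objective: "To assess quality of life following completion of SBRT in combination with Nelfinavir". Section 15.6 names the instrument, "Quality of life will be assessed using the Brief Pain Inventory form", and the variable, "An overall score will be calculated pre-treatment and at the time of the 2" (the sentence goes on to the second radiologic reassessment). The whole analysis is then one sentence: "The change in score will be evaluated with a paired t-test". Neither 15.6 nor 15.1.2 says how the overall score is formed.

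The form in Appendix I has these parts:

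- Items 3 to 6 rate pain from 0 to 10.
- Item 7 is free text: "What treatments or medications are you receiving for your pain".
- Item 8 asks "how much relief have pain treatments or medications provided", as a percentage.
- Item 9, parts A to G, opens "Circle the one number that describes how, during the past 24 hours, pain has interfered with your" and lists seven activities.

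The calendar in section 10 lists a medication review before the study and at most follow-up visits. Its footnote i makes procedures from month 3 optional, apart from interval history and adverse event evaluation. No section gives item 7, item 8 or the medication review a stated role in the analysis of the score.

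**The concern.** The synopsis gives the control group as not applicable, so nothing in the design separates the regimen's effect on pain from that of other pain treatment. Such treatment is foreseeable. Patients with bone metastases are eligible (5.1.2), and sections 5 and 6.7 allow chemotherapy or conventional radiotherapy at progression or from 4 weeks after treatment. The second score comes later than that: at 12 weeks if the 4-week assessment in 11.1 counts as the first, or at 6 months if only the required scans in 6.3 count.

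A patient whose score falls after analgesics are added pulls the mean towards improvement. A patient who needs fewer analgesics at the same pain level contributes no change.

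The second part is the label. Section 12.5.1 states: "The most frequently reported adverse event among patients receiving VIRACEPT was diarrhea". Section 12.4 lists dysphagia, nausea, vomiting, anorexia and weight loss with SBRT. No item asks about any of these, yet the result would be reported as quality of life.

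**Working it through.** **No planned figure to reproduce.** The documents give no SD, effect size, alpha or power for this test. What follows shows sensitivity only.

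**Inputs.** From the documents: 42 patients and 15% dropout (15.2), so 42 × 0.85 = 35.7, about n = 36 with both forms. Assumed: SD of change s = 2.5 points on a 0–10 scale (2.0 as a check), two-sided 0.05, no true regimen effect, and a random fraction f of patients whose score drops D points through added analgesics.

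**Formulas.** Mean change m = −f × D. Variance of change = s² + f(1 − f)D². SE = √(variance/n). With the 5% t value of 2.03 on 35 df, P(declared improvement) ≈ Φ(|m|/SE − 2.03).

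**Example, f = 0.2, D = 2.** m = −0.4. Variance = 6.25 + 0.16 × 4 = 6.89. SE = 2.625/6 = 0.4375. P ≈ Φ(0.914 − 2.03) = Φ(−1.116) = 13%. Simulation gives 14%.

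| f | D | Mean change | False improvement, simulated (s = 2.5) |
|---|---|---|---|
| 0 | – | 0 | 2.5% |
| 0.15 | 1.5 | −0.225 | 7% |
| 0.20 | 2 | −0.4 | 14% |
| 0.30 | 2 | −0.6 | 26% |
| 0.40 | 3 | −1.2 | 67–68% |

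With s = 2.0, the rows with D = 2 become about 18% and 35%.

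**If added analgesics follow a rise in pain.** Let pain rise r points first, so the net shift is f(r − D). At f = 0.3, D = 2:

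- r = 1: 0.3 × (1 − 2) = −0.3, false improvement about 10%.
- r = 2: net shift 0, nominal 2.5%.
- r above 2: the sign reverses and the bias runs towards worsening.

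**If analgesics are reduced.** With a true benefit of 1 point and no change in analgesics, SE = 2.5/6 = 0.417 and power ≈ Φ(2.40 − 2.03) = 64%. If 30% of patients cut analgesics and give back 2 points, m = −1 + 0.6 = −0.4, SE = √(6.25 + 0.21 × 4)/6 = 0.444, and power ≈ Φ(0.90 − 2.03) = 13%.

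**A tempting remedy, checked.** One could set a fall to zero change whenever pain treatment increased. With f = 0.3 and D = 1 and no regimen effect, simulation gives about 7% false worsening against 2.5% nominal, because falls are removed and rises are kept. For a true 1-point benefit, the chance of detection is 36%, against 64% when analgesics do not change.

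**Content of the score.** Items 3–6 rate pain, item 8 rates relief and items 9A–G rate interference by pain. This part needs no assumption.

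**The case against.** The plan names the Brief Pain Inventory openly, so no reader is misled about the instrument. The objective concerns quality of life after treatment and carries no hypothesis, alpha or decision rule. The percentages above rest on assumed inputs. Pain is not an eligibility criterion, so patients who start near 0 cannot fall by 2 or 3 points. Item 7 does not ask dose, so a higher dose of the same drug may go unseen. All of this stands, and it limits how strongly the point can be put.

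Four stronger readings are tempting and are not supported:

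- **That a patient with more painkillers is counted as improved.** The t-test estimates a mean and classifies nobody. Such a patient contributes improvement only if the score falls.
- **That the plan attributes the whole change to the regimen.** The objective does not say so. The uncontrolled pre/post design only invites that reading.
- **That the score is certainly unadjusted.** It is undefined. If item 8 enters it, some response to analgesics is already inside.
- **That non-pain toxicity would be hidden.** Toxicity is its own secondary objective, summarised by type and grade, with adverse event evaluation scheduled in both nelfinavir cycles and at follow-up. The last 7-day cycle begins the day after SBRT, so any instrument given at 12 weeks or later could miss diarrhea during dosing.

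None of this gives the pain-treatment data a role in the analysis or widens what the items measure.

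**Conclusion.** Two limited conclusions hold. First, without the pain-treatment data a change in mean score cannot be separated from changed analgesia or other pain treatment. The bias may run either way, and the documents do not allow it to be sized. The figures above hold only under the stated n, SD, f, D and r. Across the false-improvement settings shown for s = 2.5, the rate runs from nominal to about 68%, and if pain rises by more than the analgesics remove, the bias points to worsening. Second, the score can support a statement about pain and pain interference, not about quality of life in general.

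The point concerns one secondary endpoint. The primary analysis of freedom from local progression, the safety run-in and the toxicity stopping rule are unaffected. It is worth acting on because the change is cheap and alters what may be concluded.

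**What to change.** 1. In 3.2, 15.1.2 and 15.6, call the endpoint pain and pain interference. Define the scores, for example the mean of items 3–6 for severity and the mean of items 9A–G for interference. Draw no general quality-of-life conclusion.
2. Keep the paired t-test on the change in score.
3. Code item 7, with the medication review where it was done, as pain treatment increased, unchanged or decreased since baseline, using a rule fixed before analysis. Report the number of patients and mean score change in each category.
4. Add a prespecified sensitivity analysis that treats increases and decreases alike. One option is a combined category. Improved would mean a lower score without more pain treatment, or less pain treatment without a higher score. Worsened would be the mirror image, and all other patterns would be neither.
5. State that a fall in mean score will not be attributed to the regimen if it does not persist in that analysis. Persistence would still not prove attribution, because there is no control arm.
6. Do not use the one-sided zero-change rule as the main test.

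Cost: wording in three sections and a small coding task on data the form already collects, with no new visits. Free-text entries may lack dose, so some increases or decreases will be missed, and the claim becomes narrower.

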### 6.3 Follow-Up Procedures

Subsequent to SBRT, patients will be followed clinically for toxicity and interval history at Months 1, 2, 3, 6, 12, and every 6 months thereafter until 3 years post SBRT. A detailed medical and physical examination will be performed at 4 weeks, 3 months, 6 months and 1 year post SBRT. The following procedures are optional at Months 1, 3, 6 and every 6 months through 3 years post SBRT:

- A complete blood count (CBC) and comprehensive chemistry panel
- CT scan or MRI including the treated site (Note: this is required at Months 3 and 6 for the reason noted below)
- Physical Exam and ECOG Performance Status

PET-CT will be recommended at 3 months, 6 months, and annually thereafter however all are optional.

CT scans at 3 and 6 months will be used to determine radiographic response based on RECIST 1.1 criteria.

All follow-ups may be conducted by telephone for patient convenience. Study staff will request any of the optional procedures noted above that were performed by local physicians to be forwarded for study records.

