## 11. MEASUREMENT OF EFFECT

### 11.1 Antitumor Effect-Solid Tumors

For the purposes of this study, patients should be re-evaluated for response 4 weeks after the initial treatment, 12 weeks after treatment, 24 weeks after treatment, and every 24 weeks thereafter.

Response and progression will be evaluated in this study using the new international criteria proposed by the Response Evaluation Criteria in Solid Tumors (RECIST 1.1) Committee (30). Changes in only the largest diameter (unidimensional measurement) of the tumor lesions are used in the RECIST criteria.

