#### **15.1.2 Secondary Objectives**

- To describe the toxicity of SBRT combined with Nelfinavir delivered for the population enrolled using grading with CTCAE v. 4.0
- To determine the local control at 6 months after SBRT is delivered to a dose of 15 Gy in 1 fraction (per lesion rate) combined with Nelfinavir in patients with oligometastatic disease.
- To assess long-term clinical outcomes of this patient population after completion of SBRT and Nelfinavir by measuring progression-free survival and overall survival. Progression-free survival will be measured from time of enrollment to date of disease progression or death. Patients who are lost to follow-up will be censored for determination of progression-free survival on the date of their last evaluation. Overall survival is defined as time from enrollment to death due to any cause.
- To assess quality of life following completion of SBRT and Nelfinavir using pre- and post-SBRT completion of the Brief Pain Inventory form which will be filled out by the patient at the treatment response intervals outlined above.

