### **15.2 Sample Size/Accrual Rate**

The primary endpoint will be freedom from local progression at 6 months. The treatment regimen would be considered of insufficient activity for further study in this population

if the 6-month FFLP rate is 70% or less, and the minimum required level of efficacy that would warrant further study with the proposed regimen is a 90% FFLP at 6 months. The accrual rate is 3 patients per month, and the patients will be followed for up to 3 years. A total of 42 patients will be entered in the study accounting for a 15% dropout rate. This study would have 90% power to detect an improved 6-month FFLP from 70% to 90% using a two-sided test at significance level 0.05. Alternatively, this corresponds to the power to detect a reduction of hazard rate from 0.06 to 0.02, a reduction of 70% in hazard rate.

There will be no interim analysis for futility, since the progression endpoint will not have been reached by a meaningful number of patients before full accrual.

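### The paired t-test on pain scores keeps only patients with both forms and ignores the interim scores; about 15% are lost on the plan's own dropout allowance, with bias toward improvement if those who leave are in worse pain

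*Combined protocol and SAP*

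**What the plan says.** Protocol section 15.6 plans one quality-of-life comparison. "An overall score will be calculated pre-treatment and at the time of the" second radiologic reassessment, and then: "The change in score will be evaluated with a paired t-test". The section names no quality-of-life population, no rule for deaths or missing forms, and no sensitivity analysis.

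Section 15.1.2 collects more than that test uses. The form is one "which will be filled out by the patient at the treatment response intervals outlined above". Section 11.1 gives those intervals: "patients should be re-evaluated for response 4 weeks after the initial treatment, 12 weeks after treatment, 24 weeks after treatment", and every 24 weeks after that.

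The second reassessment has no date. In the order of section 11.1 it is week 12. If only the scans that section 6.3 requires are counted ("CT scans at 3 and 6 months will be used to determine radiographic response"), it is month 6.

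On expected loss, section 15.2 says: "A total of 42 patients will be entered in the study accounting for a 15% dropout rate". It gives no period for the 15% and does not say whether deaths are included. Section 6.10 follows withdrawn patients for survival only. The study calendar in section 10 has no row for the pain form. From month 3 its footnotes allow telephone visits and make everything optional except interval history and adverse event evaluation (with imaging required at months 3 and 6).

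**The concern.** A paired t-test needs both scores from each patient. Those without the second score leave the analysis, and any week-4 score they gave is not used. In metastatic disease it is reasonable to worry that they are the patients whose pain was getting worse. If so, the mean change among completers is more favourable than the mean change among all treated patients, and a single-arm trial has no comparator in which the same selection would occur.

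At stake is one stated secondary objective: the report could claim that pain improved when it did not. The decision on further study rests on 6-month freedom from local progression, which this does not touch.

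**Working it through.** **The plan's figure.** 42 × (1 − 0.15) = 35.7, so about 36 patients are expected to be evaluable. The 42 was sized for the primary endpoint. At 36 patients, a one-sample test of the 6-month Kaplan-Meier estimate on the log(−log) scale has 88% power, close to the stated 90%. The plan gives no number of pairs and no power for the quality-of-life test.

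**Share without a second score.** The only survival figure available is the 50.4% two-year survival in section 4.6, from a cited liver trial. It is background, not a planning assumption. With t in months and constant rates:

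- deaths D = 1 − 0.504^(t/24)
- dropout W = 1 − 0.85^(t/6) if the 15% is reached by month 6, or 1 − 0.85^(t/36) if it is spread over 3 years
- lost = 1 − (1 − D)(1 − W)

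| Reading | D | W | Lost | Pairs of 42 |
|---|---|---|---|---|
| Dropout allowance alone | – | 15% | 15% | 35.7 |
| Week 12, 15% spread over 3 years | 7.6% | 1.2% | 8.7% | 38.3 |
| Week 12, 15% reached by month 6 | 7.6% | 7.2% | 14.2% | 36.0 |
| Month 3, 15% reached by month 6 | 8.2% | 7.8% | 15.4% | 35.5 |
| Month 3, all 15% already gone | 8.2% | 15% | 22.0% | 32.8 |
| Month 6, all 15% plus deaths | 15.7% | 15% | 28.4% | 30.1 |

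If the 15% already includes deaths, the prorated loss at week 12 is lower (7.2% or 1.2%). Forms not returned after telephone visits would raise every row.

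**Bias of the paired mean.** Bias = share missing × (mean change in missing − mean change in observed patients). The second factor is not in the documents. On the 0-10 scale:

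- leavers 2 points worse: 0.15 × 2 = 0.30 toward improvement at 15% missing, and 0.22 × 2 = 0.44 at 22%
- leavers 1 point worse: 0.15 and 0.22
- leavers no different: 0
- leavers 1 point better: 0.15 and 0.22 toward worsening

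**Effect on the test.** I simulated 20,000 trials of 42 patients per setting. Assumptions: no true change, SD of change 2.5, correlation 0.7 between the 1-month and the later change, and the log-odds of a missing score rising with the 1-month change by 0.5 or 1 per SD. Negative bias means apparent improvement. The false-improvement rate is one-directional, nominal 2.5%.

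| Missing | Bias, slope 0.5 | False improvement | Bias, slope 1 | False improvement |
|---|---|---|---|---|
| 9% | −0.08 | 3.9% | −0.15 | 5.5% |
| 15% | −0.13 | 4.8% | −0.23 | 7.9% |
| 22% | −0.19 | 6.3% | −0.34 | 11.9% |
| 28.4% | −0.24 | 7.6% | −0.42 | 15% |

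For scale, the standard error at 15% missing is 2.5/√35.7 = 0.42. With random loss (slope 0) the bias is 0 and the rate 2.5%. With correlation 0.5 and slope 1 at 15% missing, they are −0.17 and 6.0%.

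**What the interim score recovers.** Bringing in the 1-month change by regression cut the bias to within 0.01 in every setting above, with no loss of precision. That result is favoured by the set-up, because loss was made to depend on the score being used. When loss depends instead on the unseen later score (15% missing, slope 1), the paired bias is −0.33 and the regression estimate −0.18: roughly halved, not removed.

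**The case against.** The strongest reply is that the documents contain no pain data on patients who leave. A reader might infer that the reported pain change will look better than it was. The documents do not support that as a fact: the sign depends on who leaves, and the bias is zero if leavers resemble completers. This stands, so the direction is stated here only as a condition.

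A reader might also infer that up to 28% loss follows from the plan's figures. It does not. It takes deaths from a trial limited to liver tumours, whereas this trial also enrols bone, lung and node disease and requires a life expectancy of at least 9 months. It adds those deaths to a 15% that may already contain them, and it takes the month-6 reading although section 11.1 points to week 12. Only the 15% is the plan's own. Nor is the analysis simply one of survivors: living patients who withdraw or return no form are dropped as well.

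A mixed model has limits too. It assumes that missing scores are explained by earlier ones, and it implicitly carries pain scores past death unless the treatment of deaths is described. Fitted to every visit over 3 years, it would have about 9 time points, and an unstructured covariance would need 9 × 10/2 = 45 parameters for 42 patients. A lag-based covariance does not suit unequally spaced visits. These objections stand and shape the fix.

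Finally, this is an unpowered secondary endpoint with no decision attached. That limits how much the point matters, but a better analysis of scores already scheduled costs little.

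**Conclusion.** The point holds in a limited form. The planned test is a completers-only comparison at an undated visit, with no provision for deaths or missing forms, and it ignores interim scores that section 15.1.2 schedules. Expected loss is about 15% on the plan's own allowance and about 9-22% across readings at week 12 to month 3.

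If loss is linked to worsening pain, the estimate is biased toward improvement by about 0.1-0.3 points and the one-directional false-positive rate is about 4-12% instead of 2.5%. These sizes rest on an assumed SD of 2.5, a correlation of 0.7 and the assumed link between early worsening and loss. If leavers do not differ, there is no bias. The change is worth making, but the primary analysis is unaffected.

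**What to change.** In section 15.6:

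1. Date the second reassessment: week 12 as in section 11.1, or month 6.
2. Make the main analysis a linear mixed model (REML, visit as a factor, baseline as one of the repeated scores, Kenward-Roger degrees of freedom). Use the scheduled scores from baseline up to and including that visit only, with unstructured covariance. That is 3 visits and 6 covariance parameters for week 12, or 4 visits and 10 parameters for month 6.
3. Report the change at that visit with its 95% interval. State that it assumes missing scores are explained by earlier scores, and describe how deaths are treated.
4. Show deaths and missing forms by visit.
5. Add one sensitivity analysis that assumes a worse change in patients with missing scores, for example 1 and 2 points worse.
6. Keep the paired t-test as a completers-only supporting analysis.

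The cost is SAP wording and slightly more analysis work, plus reliance on a missing-at-random assumption. No new data are needed if the forms are collected as section 15.1.2 says; adding a row for the form to the section 10 calendar would make that explicit.

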## 1. PROTOCOL SYNOPSIS

TITLE	Single-Arm Phase II Study of Stereotactic Body Radiation Therapy Concurrent with Nelfinavir for Oligometastases
STUDY PHASE	Phase II
INDICATION	Patients presenting with oligometastatic disease, where metastases are limited in number and location.
PRIMARY OBJECTIVES	
 
To determine the 6-month freedom from local progression rate of the radiosensitizer Nelfinavir used concurrently with 15 Gy of stereotactic body radiation therapy (SBRT) delivered in 1 fraction (per lesion) in patients with oligometastatic disease
 

SECONDARY OBJECTIVES	
 
To assess the toxicity of the radiosensitizer Nelfinavir used concurrently with 15 Gy of stereotactic body radiation therapy (SBRT) delivered in 1 fraction(per lesion) in patients with oligometastatic disease
 
To determine local control at 6 months after SBRT delivered to a dose of 15 Gy in 1 fraction (per lesion) combined with Nelfinavir in patients with oligometastatic disease
 
To assess long-term clinical outcomes of this patient population after completion of SBRT in combination with Nelfinavir
 
To assess quality of life following completion of SBRT in combination with Nelfinavir
 
To determine the correlation between phospho-Akt levels and lesion response rate
 

HYPOTHESES	Concurrent SBRT and Nelfinavir will achieve greater than 70% freedom from local progression 6 months.
STUDY DESIGN	Patients with metastatic lesions of the lung, liver, or bone will be candidates for treatment. Within three weeks of the initial treatment planning, a 15 Gy dose (per lesion) of SBRT will be administered. Prior to SBRT, patients will initiate Nelfinavir oral therapy twice daily for 7 days. Once SBRT is completed, the patient will repeat the same Nelfinavir therapy for an additional 7 days for a total of 14 days of treatment.
SAMPLE SIZE BY TREATMENT GROUP	42 patients total
SUMMARY OF SUBJECT ELIGIBILITY CRITERIA	
 
Metastasis at one or more of the following sites: bone, liver, and/or lung. No more than 5 lesions will be treated.
 
Tumor(s) to be treated is(are) <math>\leq 5.0</math> cm or <math>\leq 250</math> cm^3.
 
Age <math>\geq 18</math> years.
 
ECOG performance status <math>\leq 2</math>.
 
Histologic confirmation of malignancy (primary or metastatic tumor).
 

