#### **11.5 Response Criteria (via RECIST 1.1)**

##### **11.5.1 Evaluation of Target Lesions**

Complete Response (CR): Disappearance of all target lesions

Partial Response (PR): At least a 30% decrease in the sum of the longest diameter (LD) of target lesions, taking as reference the baseline sum LD

Progressive Disease (PD): At least a 20% increase in the sum of the LD of target lesions, taking as reference the smallest sum LD recorded since the treatment started or the appearance of one or more new lesions

Stable Disease (SD): Neither sufficient shrinkage to qualify for PR nor sufficient increase to qualify for PD, taking as reference the smallest sum LD since the treatment started

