#### 11.5.5 Clinical Response Parameters

**Time to Local Progression (TTLP)** is defined as the elapsed time from the start of treatment to the date of documented local progression or death, whichever happens earliest.

**Progression-Free Survival (PFS)** is defined as the time from starting treatment to the time of first documented tumor progression or death due to any cause, whichever occurs first. Death is considered as an event here. For subjects whose disease does not progress or who do not die, PFS will be censored at the time of the last visit.

**Time to Progression (TTP)** is defined as the time from starting treatment to the time of first documented tumor progression. Subjects who do not progress will be censored at the time of the last contact. In addition, death from any cause will also be censored.

**Overall Survival (OS)** is defined as the time from starting treatment until death due to any cause. For subjects who do not die, time to death will be censored at the time of last contact.

**Locoregional Control (LRC)** is defined as the time from starting treatment until local and/or regional relapse is documented

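### The phospho-Akt objective names lesion response rate, but the only planned phospho-Akt analysis uses PFS, so the stated objective has no planned analysis

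*Combined protocol and SAP*

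**What the plan says.** The objective appears twice in the same terms. The synopsis has "To determine the correlation between phospho-Akt levels and lesion response rate" and section 3.2 has "To determine the correlation between Phospho-Akt levels and lesion response rate". Section 15.1.2 restates the other secondary objectives (toxicity, 6-month local control, long-term outcomes, quality of life) and leaves phospho-Akt out.

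Section 15.6 has one statement on how phospho-Akt will be analysed: "The change of phospho-Akt levels will be correlated to progression-free survival outcome". It names Western blot as the method, which is an assay, and gives no statistical test or model. It does not say which change is meant.

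The same section plans a lesion-level analysis that does not involve phospho-Akt. Its coding rule is "The lesion will be coded as being locally controlled if it is considered stable radiographic disease", with partial and complete response also counted as control. Its method is "The proportion of the lesions that have a stable or better response will be estimated using generalized estimating equation", repeated by metastatic site.

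Sections 6.2 and 9.1 and the study calendar deal only with blood collection, processing and timing: a sample before nelfinavir, one on the day of SBRT, and an optional one at one month.

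**The concern.** An objective and its analysis should share an outcome, and these two do not. Lesion response concerns the irradiated lesions, up to five per patient. PFS is a single time per patient, and events outside the treated lesions can trigger it. The background (section 4.4) links nelfinavir's radiosensitizing effect to inhibition of phospho-Akt. That is an effect on irradiated tissue, so the lesion is the natural unit for the question.

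If the plan is followed as written, the trial reports a phospho-Akt/PFS correlation and leaves a stated secondary objective unanswered, although patients gave blood for it. Any lesion analysis added later would be specified with the data in hand.

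**Working it through.** This is a comparison of texts. The plan gives no figure for this objective, so there is none to reproduce.

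**Step 1: every mention of phospho-Akt that bears on the objective or its analysis.**

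- Synopsis and 3.2: outcome is lesion response rate.
- 15.1.2: not mentioned.
- 6.2, 9.1 and the study calendar: sampling and assay only.
- 15.6, correlative item: outcome is PFS.
- 15.6, lesion-level GEE: outcome is lesion status, with no phospho-Akt term; the only subdivision is by metastatic site.

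No section plans phospho-Akt against lesion response.

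**Step 2: can PFS stand in for lesion response?** Section 11.5.5 defines PFS as "the time from starting treatment to the time of first documented tumor progression or death due to any cause", and the progression definition in 11.5.1 includes "or the appearance of one or more new lesions". A patient whose treated lesions all respond therefore has a PFS event on developing a new lesion or dying of any cause. The reverse can also happen. Section 11.5.1 judges progression on the sum of diameters, while 15.6 evaluates each lesion independently, so one growing lesion among several may fail without the patient meeting the progression criterion. The outcomes differ in unit, in type (time to event against 6-month status) and in the events counted.

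**Step 3: is the lesion outcome already defined?** Yes, well enough to use. Section 11.5.4 counts complete response, partial response and stable disease as response. Section 15.6 codes stable or better as controlled. Section 15.8 treats only progression, early death and unknown status as failure. All three point to stable-or-better.

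**Step 4: how much could a lesion-level model show?** Phospho-Akt change has one value per patient, so the information is limited by the number of patients with a failed lesion. Inputs from section 15.2: 42 patients, 15% dropout, and 6-month freedom from local progression of 90% (worth further study) or 70% (insufficient). Assumption: one minus that rate is the proportion of patients with a failed lesion.

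- Patients: 42 × 0.85 = 35.7, taken as 36.
- Expected patients with a failure: 36 × 0.10 = 3.6, or 36 × 0.30 = 10.8.
- P(fewer than 5) = Σ C(36,k) p^k (1−p)^(36−k) for k = 0 to 4. At p = 0.10 the terms are 0.023 + 0.090 + 0.175 + 0.221 + 0.202 = 0.711. At p = 0.30 the sum is 0.0071.
- With all 42 patients: expected failures 4.2 and 12.6; P(fewer than 5) = 0.588 and 0.0015.
- Standard error of the log odds ratio per SD of phospho-Akt change, patient-level approximation, 36 patients: 1/√(36 × 0.10 × 0.90) = 0.556, so the 95% limits are the estimate times or divided by exp(1.96 × 0.556) = 2.97. At 30% failure: 1/√(36 × 0.30 × 0.70) = 0.364, a factor of 2.04.

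Fewer than 5 is used here only as a yardstick for sparse data.

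**The case against.** The best defence is that this is a small correlative item in a 42-patient single-arm study. PFS is a legitimate exploratory correlate, and rewording the objective would remove the contradiction in one line. All of that stands. It limits the severity, but it does not supply the missing analysis, and rewording would give up the lesion question.

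Three stronger readings are tempting, and the documents do not support them.

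- **That lesion response is undefined.** A reader might infer this because 3.2 lists local control and lesion response as separate objectives, which could suggest complete plus partial response for the latter. Separate listing is the only support for that reading, and 11.5.4, 15.6 and 15.8 all point to stable-or-better. Complete plus partial response would also fit poorly, since partial response needs a measured 30% decrease and 11.3 classes bone lesions as non-measurable.
- **That the PFS correlation would hide a local effect by a calculable amount.** New lesions and unrelated deaths would tend to dilute a purely local signal. The amount depends on non-local event rates and an effect size that the documents do not give.
- **That missing scans make a lesion analysis unworkable without a new rule.** Section 6.3 and the calendar's note h require CT or MRI at months 3 and 6, although note i makes most procedures at those visits optional. Section 15.8 counts patients of unknown status as failures but does not expressly cover lesions. How to treat lesions without a 6-month status is a question for the main lesion-level GEE, and a phospho-Akt model can follow whatever is done there.

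**Conclusion.** The mismatch is real and follows from the text alone: the stated secondary objective has no planned analysis, and the planned PFS correlation does not answer it. Severity is minor. The primary endpoint, the sample size, the safety run-in and the stopping rule are unaffected.

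The remedy has limited yield. On the assumptions of 36 patients and a failed-lesion proportion equal to one minus the 6-month rate in 15.2, sparse failures are likely at 90% (71%) and unlikely at 70% (0.7%). The lesion-level result is therefore least informative if the regimen works as hoped. That is a reason to label it exploratory, and it does not justify leaving the objective without an analysis.

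**What to change.** In section 15.6, add one exploratory lesion-level GEE logistic model clustered by patient:

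- **Lesions and outcome:** the same lesions and the same 6-month stable-or-better coding as the main lesion-level GEE, consistent with 11.5.4.
- **Covariate:** only the change in phospho-Akt from the pre-nelfinavir sample to the first SBRT-day sample. Neither sample is optional, and specifying the first SBRT day matters because 6.2 allows repeat rounds.
- **Report:** an odds ratio with 95% confidence interval using small-sample standard errors. If there are too few failures to fit the model, describe phospho-Akt change by lesion outcome instead.
- **Lesions without a 6-month status:** handled exactly as in the main lesion-level GEE.

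Keep PFS as an additional exploratory correlate, and add the objective to 15.1.2.

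The cost is a short paragraph in 15.6, a line in 15.1.2 and one extra model on data already collected. The downside is an imprecise result that may be descriptive only. The alternative of rewording the synopsis and 3.2 to name PFS is simpler, but it abandons the lesion question.
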